7.7.9 Additional Target Lesion Treatment (if required)

Following mandatory post-dilatation, additional IVL treatment may be delivered if areas of non-dilatable residual stenosis > 50% remain. This may be done using the commercially available Shockwave M⁵, M⁵⁺ (where applicable) or S⁴ IVL catheters – or additional pulses with the same Mini S IVL catheter configuration used for treatment in section 7.7.7 may be delivered.

	No.: CP 65324	REV. D
	TITLE: Mini S Feasibility Study Protocol	
	CLASS: CLINICAL PROTOCOL	

7.7.10 Destination Therapy

Destination therapy is allowed at the discretion of the Investigator. Destination therapy may include commercial IVL, bare-metal stent (BMS), drug-eluting stent (DES), drug coated balloon (DCB) or Tack implant.

A BMS, DES, DCB or Tack implant is allowed for the following PTA failures:

- Residual stenosis \geq 50% by visual estimate, or
- Un-resolved flow-limiting (\geq Grade D) dissection, or
- Trans-lesional gradient >10 mm Hg is observed.

If this treatment is performed at the time of procedure, it is considered standard of care to maximize acute luminal gain and does not meet the definition of serious deterioration in the SAE definition (Section 10.1.2).

All dissection Type/Grade A, B, and C must be documented as an adverse event. Dissection Type/Grade D, E, and F must be documented as a SAE.

The 4th and final required angiographic cine should be acquired after all endovascular procedures on the target lesion are complete.

7.8 Follow-Up

7.8.1 Discharge or Within 12-24 Hours Post-Procedure

The following assessments and procedures will be performed within **12-24 hours** post procedure or prior to hospital discharge, whichever occurs first:

- Review of anticoagulation/antiplatelet medications
- Adverse event assessment

7.8.2 30-Day Follow-Up

The following evaluations will be performed at **30 days** (-7/+14 days) post procedure:

- Physical examination
 - Vital signs
- ABI or TBI of target limb (at rest; keep consistent with screening)
- Rutherford Category of target limb
- Review of anticoagulation/antiplatelet medications
- Adverse event assessment

Note: If treatment of two target lesions is planned across both limbs, the Rutherford Category and ABI/TBI for each limb must be assessed. If ABI/TBI cannot be assessed due to non-compressible vessels, this should be documented.

	No.: CP 65324	REV. D
	TITLE: Mini S Feasibility Study Protocol	
	CLASS: CLINICAL PROTOCOL	PAGE 33 OF 70

7.8.3 6-Month Follow-Up

The following evaluations will be performed at **6 months** (180 +/-30 days) post procedure:

- Physical examination
 - Vital signs
- ABI or TBI of target limb (at rest; keep consistent with screening)
- Rutherford Category of target limb
- Review of anticoagulation/antiplatelet medications
- Adverse event assessment

Note: If treatment of two target lesions is planned across both limbs, the Rutherford Category and ABI/TBI for each limb must be assessed. If ABI/TBI cannot be assessed due to non-compressible vessels, this should be documented.

7.8.4 12-Month Follow-Up

The following evaluations will be performed at **12 months** (360 +/-30 days) post procedure:

- Physical examination
 - Vital signs
- ABI or TBI of target limb (at rest; keep consistent with screening)
- Rutherford Category of target limb
- Review of anticoagulation/antiplatelet medications
- Adverse event assessment
- Duplex ultrasound (DUS)

Note: If treatment of two target lesions is planned across both limbs, the Rutherford Category and ABI/TBI for each limb must be assessed. If ABI/TBI cannot be assessed due to non-compressible vessels, this should be documented.

7.8.5 Prior to Target Limb Revascularization

If a target limb revascularization procedure is performed during the follow-up period, angiographic images acquired as standard of care should be submitted to the core lab for purposes of adjudication.

7.9 Subject Withdrawal

A study subject has the right to discontinue participation at any time without penalty or loss of benefits to which the subject is otherwise entitled. A subject that has withdrawn from the study will be treated according to standard of medical care and will not be replaced.

	No.: CP 65324	REV. D
	TITLE: Mini S Feasibility Study Protocol	
	CLASS: CLINICAL PROTOCOL	PAGE 34 OF 70

7.9.1 When and How to Withdraw Subjects

Subjects may be withdrawn with the medical discretion of the physician, or they may voluntarily withdraw their consent at any time without impact to their medical treatment. When a subject is withdrawn, all data obtained prior to the time of withdrawal may be submitted to the Study Sponsor and be included in the study database, unless otherwise requested by the subject in writing.

In the event a subject is lost to follow-up or cannot be contacted for post-treatment assessments, at least three attempts (two phone calls and a certified letter) will be made to locate the study subject, and these efforts will be documented. If the subject cannot be located, the subject's lost to follow-up status will be documented in the EDC and they will be exited from the study.

Should the subject expire, adverse event and study exit/withdrawal forms should be completed. Physician assessment is required to determine if the cause of death was possibly or definitely related to the Mini S Peripheral IVL Catheter. If available, copies of the death certificate and/or an autopsy report should be included in the research records. The Investigator may need to provide written notification to the IRB/EC upon the death of the study subject, dependent on the IRB/EC policies. Associated regulatory bodies may also be required to be notified depending on local jurisdiction and relatedness to the study device and procedures.

	No.: CP 65324	REV. D
	TITLE: Mini S Feasibility Study Protocol	
	CLASS: CLINICAL PROTOCOL	PAGE 35 OF 70

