7.7.4 Definition of Enrollment

The definition of enrollment is when the subject signs informed consent, meets all general and angiographic eligibility criteria, a 0.014" guidewire has crossed the target lesion, and the Mini S IVL catheter has been inserted over the guidewire and into the body.

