9.0 DATA ANALYSIS PLAN

9.1 General Statistical Methods

Descriptive statistics will be provided in this study. Analyses will be conducted at pre-specified time points including 30 days, 6 and 12 months post procedure.

Categorical variables will be summarized by the number of observations available, frequency, and percentage. Unless otherwise noted, missing data will be excluded from the denominator. Clinical outcomes analyzed at 30 days will be evaluated as categorical (binary) data. Exact confidence intervals will be generated for estimates of proportions.

Continuous variables will be summarized by the mean, standard deviation, median, minimum and maximum. Asymptotic confidence intervals will be generated for estimates of means.

9.2 Statistical analyses will be performed using SAS System® Version 9.4 or higher. Primary Endpoints

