9.3 Sample Size Determination

Per ISO 14155:2020 (Annex I, Section 1.4), the Mini S Feasibility study is considered to be an exploratory clinical investigation that does not have pre-specified primary hypotheses. For feasibility studies, sample sizes between 12 and 50 have been recommended [21-25]. The sample size for the Mini S Feasibility study (up to n=50) is in keeping with these published recommendations.

	No.: CP 65324	REV. D
	TITLE: Mini S Feasibility Study Protocol	
	CLASS: CLINICAL PROTOCOL	PAGE 38 OF 70

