9.4 Populations for Analysis

The primary analysis population will be the Intent-to-Treat (ITT) cohort which includes all enrolled subjects.

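### Section 7.9.1 ends follow-up at the first assessment where a subject cannot be located, and is silent on safety follow-up after physician withdrawal, so later outcomes go missing avoidably

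*Protocol*

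**What the plan says.** Protocol 7.9.1 sets three rules.

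- **Loss to follow-up.** The trigger is failure to reach a subject for post-treatment assessments, with no particular visit named. At least three documented attempts follow: two telephone calls and a certified letter. A subject who is still not located has "lost to follow-up status will be documented in the EDC and they will be exited from the study". No later attempt and no re-entry is described.
- **Physician withdrawal.** A physician may withdraw a subject on medical judgement. The section does not say whether safety follow-up then continues.
- **Data already collected.** On withdrawal, data obtained so far may be "included in the study database, unless otherwise requested by the subject in writing".

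Elsewhere, 9.4 makes the primary population the "Intent-to-Treat (ITT) cohort which includes all enrolled subjects". Section 7.7.4 places enrollment at the point where, eligibility and wire crossing being met, "the Mini S IVL catheter has been inserted over the guidewire and into the body". Section 9.1 says that, unless otherwise noted, "missing data will be excluded from the denominator", and treats 30-day clinical outcomes as binary. Section 9.5 rules out imputation for the primary analyses and censors event-free subjects at last known follow-up in time-to-event analyses. Sections 10.4.1 and 10.4.2 require AE and SAE collection from enrollment through 12 months.

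**The concern.** The investigational treatment is delivered once, at the index procedure. Exit or withdrawal afterwards cannot spare the subject any study treatment; it only stops observation.

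A subject who cannot be found around day 30 or month 6 may be reachable later, through a routine clinic visit, a readmission or a new telephone number. Under 7.9.1 nobody is required to try. The study then forgoes that subject's 12-month visit, which has the only scheduled duplex (Table 1 and 7.8.4) and so supplies the ultrasound part of primary patency (5.2), together with the later MAE assessments (5.1). A later contact could also have supplied the date of an event in the first 30 days, since onset dates are recorded on the AE form (10.4.1).

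No analysis plan can recover a visit that was never attempted. The study is first-in-human (6.3), is meant to inform a pivotal investigation (6.2), and its data are intended for regulatory submissions (12.9). It is descriptive, so the reported rates are its result.

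**Working it through.** **Plan's own figure.** There is no calculation to reproduce. Section 9.3 gives up to 50 subjects, calls the study an "exploratory clinical investigation that does not have pre-specified primary hypotheses", and states no event rate, power or dropout. All counts below except the 50 are assumptions.

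**Step 1: what happens to an exited subject.**

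| Question | Source | Answer |
|---|---|---|
| Still in the ITT cohort? | 7.7.4, 9.4 | Yes; membership is fixed at catheter insertion |
| Replaced? | 7.9 | Withdrawn subjects are not |
| Earlier data kept? | 7.9.1, 9.5 | Yes, unless a withdrawn subject asks otherwise in writing |
| Later binary outcomes? | 9.1 | Missing, so out of the denominator |
| Later time-to-event outcomes? | 9.5 | Censored at last known follow-up |
| Technical Success? | 9.2.2 | Unaffected by later loss; it uses the final procedural angiogram |

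So the analysed set shrinks while the population does not.

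**Step 2: range compatible with a 12-month proportion.** Take N = 50 enrolled, m with missing outcome and s successes among the N − m observed, with one outcome per subject for simplicity.

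- Available-case rate: s/(N − m)
- Lowest all-enrolled rate: s/N
- Highest all-enrolled rate: (s + m)/N
- Width of the range: m/N = 2 percentage points per lost subject at N = 50

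With m = 5 and s = 36, the observed rate is 36/45 = 80%. The range is 36/50 = 72% to (36 + 5)/50 = 82%.

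**Step 3: the same check for a binary MAE rate.** With x observed events, the available-case rate is x/(50 − m) and the all-enrolled range is x/50 to (x + m)/50.

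| m missing | x = 2: available-case | x = 2: all-enrolled range | x = 0: available-case | x = 0: all-enrolled range |
|---|---|---|---|---|
| 1 | 2/49 = 4.1% | 4.0% to 6.0% | 0% | 0% to 2.0% |
| 2 | 2/48 = 4.2% | 4.0% to 8.0% | 0% | 0% to 4.0% |
| 3 | 2/47 = 4.3% | 4.0% to 10.0% | 0% | 0% to 6.0% |
| 5 | 2/45 = 4.4% | 4.0% to 14.0% | 0% | 0% to 10.0% |

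For x = 2 and m = 3, the exact (Clopper-Pearson) 95% intervals are 0.5% to 14.5% for 2/47, 0.5% to 13.7% for 2/50, and 3.3% to 21.8% for 5/50. The interval that would be reported does not reflect the uncertainty from missing outcomes.

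**Step 4: direction.** Suppose the full-cohort rate is 2/50 = 4.0% and one subject's outcome is missing. If that subject was event-free, the reported rate is 2/49 = 4.1%, slightly too high. If that subject had the event, it is 1/49 = 2.0%, too low. The protocol gives no basis for choosing between these cases.

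**The case against.** The other side is strong on several points.

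- **Cohort membership.** A reader might infer that exited subjects leave the ITT cohort, or that 7.9.1 contradicts 9.4. The documents do not support either reading. Exit ends follow-up, and an ITT definition says who is counted without guaranteeing data for everyone. A subject whose data are removed is still an enrolled subject, with missing data.
- **Direction of bias.** A reader might also infer that the losses flatter the device, because subjects with poor results disengage. Nothing in the protocol shows this, and Step 4 shows that the shift can go either way.
- **Source of the effect.** The shrinking denominator comes from 9.1 and 9.5, not from 7.9.1, and sensitivity analyses for missing data belong in an SAP that is not at hand. This stands for the analysis. It does not answer the point that 7.9.1 creates missingness that need not occur.
- **Three attempts are reasonable diligence.** They are, for one visit. It is also speculative to say that a given subject would be reachable later. But the rule makes exit mandatory and schedules no further attempt, so the possibility is never tested.
- **Data removal on request.** This is an ethics choice, and it fits 12.9.1, which allows participants a part in governing their data and defers to local ethics guidelines. It should not be barred on statistical grounds.
- **Stakes.** The study is exploratory, with no hypothesis test, so no pass/fail result can flip.

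**Conclusion.** The point holds as a low-cost improvement to conduct, not as an error in the analysis population. Section 7.9.1 does not limit lost-to-follow-up exit to the end of the study. It also leaves safety follow-up after physician withdrawal unstated, while 10.4.1 and 10.4.2 expect event collection to 12 months. The exposed outcomes are 12-month duplex patency and 6- and 12-month MAE. For subjects lost before day 30, it is also the chance to establish 30-day MAE status afterwards. Technical Success is not exposed to loss to follow-up.

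At 50 enrolled, the range widens by 2 percentage points per lost subject, or 10 points for an assumed five losses (72% to 82% around an observed 80%). The numbers lost, the event counts and the one-outcome-per-subject simplification are assumptions; the protocol gives no dropout rate. The share of losses that renewed contact would recover is unknown.

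**What to change.** Revise 7.9.1 as follows.

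1. Record failure to reach a subject as a missed visit. Attempt contact again at each scheduled visit, and assign lost-to-follow-up status only when the 12-month window closes. Where consent allows, use treating-hospital records for vital status, reintervention and amputation. Table 1 centres that window on day 365 and 7.8.4 on day 360, both ±30 days, so the closing day is 395 or 390; the two must be reconciled.
2. State that after withdrawal by a physician, safety follow-up to 12 months continues unless the subject withdraws consent, in line with 10.4.1 and 10.4.2.
3. Keep the written data-removal option where ethics committees require it, and report the number of enrolled subjects whose data were removed next to the ITT count.

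The cost is a protocol and consent wording change and a few extra contact attempts per unreachable subject. No endpoint, sample size or analysis method changes.

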8.0 BENEFITS AND RISKS

8.1 Benefits

There may be no additional benefit from participation since patients can receive IVL treatment with a commercially available device per standard of care. The study will provide safety and performance data associated with treatment of calcified arteries using the Mini S IVL Catheter. These clinical results may inform physicians in determining the optimal treatment strategy for this patient population.

8.2 Risks

For detailed information on the risks of the device(s) used in the study procedure, including a complete list of contraindications, warnings, precautions, and potential adverse effects, please refer to the Instructions for Use (IFU) for the Mini S Peripheral IVL Catheter. It is important to ensure that the IFU referred to represents the generation of the device used in the study procedure. Unanticipated risks can occur.

Possible adverse effects are consistent with standard intravascular procedures. Risks identified as unique to the device and its use are outlined in the IFU for the Mini S Peripheral IVL Catheter. They include:

- Allergic/immunologic reaction to the catheter material(s) or coating
- Device malfunction or failure

8.3 Risks Associated with Participation in the Clinical Investigation

All assessments are considered to be standard of care but may be conducted more frequently to comply with the follow-up visit schedule. Non-invasive assessments at follow-up visits include physical exams, ABI/TBI, Rutherford Category assessments, and duplex ultrasounds. All pose minimal risk to the patient. For procedure-related risks, please refer to the current IFUs.

Risks associated with the management of privacy and confidentiality with the sharing of data exist for subjects participating in research studies. To mitigate these risks, each subject in the study will be assigned a specific study identification code that shares no identifiable factors with the Sponsor. Only hospital staff and the CRO will be privy to information that links the subject's identifiable information to this subject code. De-identified data (data that is attributed to the subject's study identification code) will be uploaded into a password protected Electronic Data Capture (EDC) system. This EDC can only be accessed by suitably trained and allocated members of the study team (site Investigators, Study Coordinators, personnel associated with the CRO and relevant personnel at the Sponsor organization).

8.4 Possible Interactions with Concomitant Medical Treatments

There are no known possible interactions within this study.

	No.: CP 65324	REV. D
	TITLE: Mini S Feasibility Study Protocol	
	CLASS: CLINICAL PROTOCOL	

8.5 Mitigation of Risks

Only those patients meeting each inclusion and no exclusion criteria will be enrolled into this study. Investigators will be qualified by education, training and experience to assume responsibility for the proper conduct of the clinical investigation. Risks of observed or theoretical adverse events will be mitigated through the Instructions for Use, physician training, patient selection in the study protocol, and close monitoring of protocol adherence.

All efforts will be made to minimize risks specifically by:

- Site selection
- Ensuring compliance to the protocol and IFU
- Assignment of study identification code to protect privacy and ensure confidentiality
- Study monitoring
- Safety processes – protocol adverse event reporting requirements, CEC and DSM oversight, and safety reporting to regulatory authorities including Vigilance reporting
- Review of all device malfunctions and complaints by Quality. Risk acceptability thresholds and trend identification methods have been established, and actions will be taken if those are met.

	No.: CP 65324	REV. D
	TITLE: Mini S Feasibility Study Protocol	
	CLASS: CLINICAL PROTOCOL	PAGE 37 OF 70

9.0 DATA ANALYSIS PLAN

9.1 General Statistical Methods

Descriptive statistics will be provided in this study. Analyses will be conducted at pre-specified time points including 30 days, 6 and 12 months post procedure.

Categorical variables will be summarized by the number of observations available, frequency, and percentage. Unless otherwise noted, missing data will be excluded from the denominator. Clinical outcomes analyzed at 30 days will be evaluated as categorical (binary) data. Exact confidence intervals will be generated for estimates of proportions.

Continuous variables will be summarized by the mean, standard deviation, median, minimum and maximum. Asymptotic confidence intervals will be generated for estimates of means.

9.2 Statistical analyses will be performed using SAS System® Version 9.4 or higher. Primary Endpoints

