2.0 STUDY SUMMARY

Study Title	Prospective, Multi-center, Single-arm Feasibility Study of the Shockwave Medical Mini S Peripheral Intravascular Lithotripsy (IVL) System (Mini S Feasibility Study)
Study Objective	To assess the safety and performance of the Shockwave Medical Mini S Peripheral IVL System for the treatment of heavily calcified, stenotic peripheral arteries.
Study Device(s)	Shockwave Medical Peripheral IVL System with Mini S IVL Catheter (Standard and Flex configurations)
Indications for Use	The Mini S IVL Catheter is intended for lithotripsy-enhanced catheter dilatation of lesions, including calcified lesions found in the peripheral vasculature, such as the iliac, femoral, ilio-femoral, popliteal, infra-popliteal, and renal arteries. The Mini S IVL Catheter is not for use in the coronary or cerebral vasculature.
Study Design	Prospective, multi-center, single-arm feasibility study
Enrollment	Up to 50 subjects with a minimum of 10 BTK lesions treated at up to 6 sites in Australia and New Zealand. A maximum of two (2) target lesions may be treated per subject.
Study Duration / Follow-Up Period	Subjects will be followed through discharge, 30 days, 6 and 12 months. Duplex Ultrasound (DUS) assessments required at 12 months. Total anticipated study duration approximately 26 months.
Subject Population	Subjects with moderate to severely calcified peripheral artery disease (PAD) with target lesion located in a native, de novo superficial femoral, popliteal or infrapopliteal artery.
Primary Safety Endpoint	Major Adverse Events (MAE) at 30 days defined as a composite of: 
 ○ Cardiovascular death ○ Clinically-driven target lesion revascularization (CD-TLR) ○ Unplanned target limb major amputation (above the ankle)
Primary Performance Endpoint	Technical Success defined as final residual stenosis ≤50% without flow-limiting dissection (≥ Grade D) of the target lesion by angiographic core lab.

	No.: CP 65324	REV. D
	TITLE: Mini S Feasibility Study Protocol	
	CLASS: CLINICAL PROTOCOL	

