5.2 Performance Endpoints

The performance endpoints are listed below. Device endpoints will be reported for all Mini S IVL Catheters.

- **PRIMARY: Technical Success** defined as *final* residual stenosis \leq 50% without flow-limiting dissection (\geq Grade D) of the target lesion by angiographic core lab.
- **IVL Technical Success (post-dil)** defined as *post-dilatation* residual stenosis \leq 50% without flow-limiting dissection (\geq Grade D) of the target lesion by angiographic core lab (measured immediately following mandatory post-dilatation).
- **IVL Device Success** defined as the ability to deliver, advance across the target lesion, pressurize, pulse, flush and retrieve the Mini S IVL Catheter.
- **Technical Success (final)** defined as *final* residual stenosis \leq 30% without flow-limiting dissection (\geq Grade D) of the target lesion by angiographic core lab.
- **Primary Patency** at 12 months defined as:
 - Above the knee lesions: freedom from \geq 50% restenosis as determined by Duplex Ultrasound (DUS) and freedom from Clinically-Driven Target Lesion Revascularization (CD-TLR)
 - Below the knee lesions: freedom from both total occlusion (100% diameter stenosis by DUS) in all of the target lesions in a flow pathway, as well as a CD-TLR

	No.: CP 65324	REV. D
	TITLE: Mini S Feasibility Study Protocol	
	CLASS: CLINICAL PROTOCOL	PAGE 20 OF 70

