9.5 Handling of Dropouts or Missing Data

No imputation of or adjustments for missing data will be performed for the primary analyses. All available data will be presented. For time to event analyses, subjects who do not experience the event in question will be censored at their last known follow-up.

	No.: CP 65324	REV. D
	TITLE: Mini S Feasibility Study Protocol	
	CLASS: CLINICAL PROTOCOL	PAGE 39 OF 70

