10.4 Serious and Non-serious Adverse Event Reporting Requirements

10.4.1 AE Reporting Requirements

All AE information will be collected from enrollment through 12 months follow-up.

AEs should be reported in the subject's medical records as applicable and on the Adverse Event Case Report Form (AE CRF). Data reported should include date of onset, treatment, resolution, and an assessment of both seriousness and relationship to the study device and procedure. AEs will be followed until the event has resolved (in the case of permanent impairment, the event will be followed until it stabilizes, and the overall clinical outcome has been ascertained).

	No.: CP 65324	REV. D
	TITLE: Mini S Feasibility Study Protocol	
	CLASS: CLINICAL PROTOCOL	

Any AEs that meet IRB/EC reporting requirements must be reported per the institution's policy.

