Target Lesion Revascularization, Clinically-driven (TLR): A target lesion revascularization performed due to target lesion diameter stenosis $\geq 50\%$ and either evidence of clinical or functional ischemia (e.g., recurrent/progressive life-limiting intermittent claudication, claudication unresponsive to medical therapy, CLI) or recurrence of the clinical syndrome for which the initial procedure was performed. Clinically driven target lesion revascularization occurs in the absence of protocol directed surveillance ultrasound or angiography.

Target Vessel Revascularization, Clinically-driven (TVR), non-TLR: A target vessel revascularization performed due to non-target lesion diameter stenosis $\geq 50\%$ and either evidence of clinical or functional ischemia (e.g., recurrent/progressive life-limiting intermittent claudication, claudication unresponsive to medical therapy, CLI) or recurrence of the clinical syndrome for which the initial procedure was performed. Clinically driven target vessel revascularization occurs in the absence of protocol directed surveillance ultrasound or angiography.

Total Occlusion A 100% stenotic lesion as documented by angiographic absence of flow.

Toe Brachial Index (TBI): The ratio of systolic blood pressure measured at the toe to systolic blood pressure measured at the brachial artery.

Unanticipated Serious Adverse Device Effect (USADE): Serious adverse device effect which by its nature, incidence, severity or outcome has not been identified in the current risk assessment.

Note: Anticipated serious adverse device effect (ASADE) is an effect which by its nature, incidence, severity or outcome has been identified in the risk assessment.

Wound: Foot ulcer or gangrene. After debridement and/or minor amputation, a wound is characterized as a healed wound when it is completely epithelialized.

	No.: CP 65324	REV. D
	TITLE: Mini S Feasibility Study Protocol	
	CLASS: CLINICAL PROTOCOL	

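### Dropping missing data from the denominator suits 12-month primary patency poorly, because a recorded CD-TLR classifies a lesion without a scan while a CD-TLR-free lesion needs one

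*Protocol*

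**What the plan says.** Section 9.1 gives one rule for summarising categorical variables: "Unless otherwise noted, missing data will be excluded from the denominator". No exception for patency appears elsewhere in the protocol. Section 9.5 adds "No imputation of or adjustments for missing data will be performed for the primary analyses" and a censoring rule for time-to-event analyses, but does not say that patency is analysed that way. Section 9.1 names only the 30-day clinical outcomes as binary.

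Section 5.2 defines 12-month primary patency in two parts. Above the knee, the lesion must be free of restenosis of 50% or more on duplex and free of CD-TLR. Below the knee the wording is "freedom from both total occlusion (100% diameter stenosis by DUS) in all of the target lesions in a flow pathway, as well as a CD-TLR".

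The two parts are observed by different routes:

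- **Duplex.** It is scheduled once. Section 2.0 says "Duplex Ultrasound (DUS) assessments required at 12 months"; Table 1 (section 7.4) and section 7.8.4 agree.
- **CD-TLR.** Section 15.1 defines it without reference to the study scan: "Clinically driven target lesion revascularization occurs in the absence of protocol directed surveillance ultrasound or angiography". Event collection is continuous (section 10.4.1: "All AE information will be collected from enrollment through 12 months follow-up"), and section 13.1 has the Clinical Events Committee adjudicate revascularizations.

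**The concern.** Complete-case analysis is usually thought harmless when data are missing completely at random. That does not carry over to this composite, because the two outcomes are not equally easy to establish. One recorded CD-TLR settles failure. Success can be established only by a readable 12-month duplex. Excluding unclassified lesions therefore thins out the CD-TLR-free group and leaves the recorded CD-TLR failures in full.

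The reported proportion then depends partly on scan attendance. Section 6.2 says the study should supply information for later steps, including parameters for a pivotal investigation. A patency figure shifted by missed scans could carry into that planning, and the exact interval, which reflects sampling error only, would not show the shift.

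**Working it through.** The protocol states no patency rate, CD-TLR rate or scan-completion rate, so there is no figure of its own to reproduce. All rates below are assumptions.

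**Notation.** p = true 12-month patency; t = proportion with CD-TLR; m = share of CD-TLR-free lesions not scanned, at random; r = duplex failure rate among CD-TLR-free lesions, so p = (1-t)(1-r).

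**Proportion under 9.1, CD-TLR lesions kept as failures.**
- Numerator: p(1-m).
- Denominator: t + (1-t)(1-m) = 1 - m(1-t).
- Estimate: p(1-m)/[1 - m(1-t)].
- Bias: -pmt/[1 - m(1-t)], which is zero only if m = 0 or t = 0.

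| p | t | m | Estimate | Bias (points) |
|---|---|---|---|---|
| 70% | 15% | 10% | 0.630/0.915 = 68.9% | -1.1 |
| 70% | 15% | 20% | 0.560/0.830 = 67.5% | -2.5 |
| 70% | 15% | 30% | 0.490/0.745 = 65.8% | -4.2 |
| 60% | 10% | 10% | 0.540/0.910 = 59.3% | -0.7 |
| 75% | 25% | 30% | 0.525/0.775 = 67.7% | -7.3 |

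The last two rows are the extremes over p = 60-75%, t = 10-25%, m = 10-30%. The -7.3 corner has p = 1-t, meaning every CD-TLR-free lesion is patent. A simulation of 50 lesions (t = r = 15%, 80% scanned, 40,000 runs) gave 0.697 against 0.696 from the formula.

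**Worked counts.** Take 50 lesions, 8 with CD-TLR and 42 without, 36 of the 42 truly patent.

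| CD-TLR-free lesions scanned | Proportion under 9.1 | Exact 95% interval |
|---|---|---|
| 42 of 42 | 36/50 = 72.0% | 57.5-83.8 |
| 35 of 42 | 30/43 = 69.8% | 53.9-82.8 |
| 28 of 42 | 24/36 = 66.7% | 49.0-81.4 |

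Interval half-widths are about 13 to 16 points. For the middle row, estimating the two parts separately gives 42/50 x 30/35 = 72.0%, the true value. Counting the 7 unscanned lesions all as failed or all as patent gives bounds of 30/50 = 60% and 37/50 = 74%.

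**Departures from random missingness.** With t = r = 15%, true patency is 72.3%. Let patent lesions be scanned 80% of the time and restenosed lesions with probability q. The estimate is 0.7225 x 0.8/[0.15 + 0.85(0.85 x 0.8 + 0.15q)].
- q = 80%: 69.6% (-2.6 points).
- q about 56%: no bias.
- q = 40%: 74.2% (+1.9 points).

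**Other readings of the text, same t and r.**
- If 9.1 drops every lesion without a duplex, CD-TLR lesions included, and no CD-TLR lesion is scanned, the estimate is 1-r = 85.0% against 72.3%.
- If patency were a time-to-event analysis under 9.5 and unscanned lesions seen at 12 months stayed event-free, the estimate is 0.85 x (1 - 0.15 x 0.8) = 74.8% at 80% scanned, about 2.6 points too high.

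**The case against.** The strongest case against is that the protocol does not assign 12-month patency to the simple proportion. Only 30-day outcomes are called binary, section 9.5 anticipates time-to-event analyses, and the endpoint-level estimator may sit in a statistical analysis plan not available here. This limits the point to patency reported as a proportion. It does not remove it: 9.1 is a stated default with no exception for patency, and the 9.5 censoring rule would not by itself remove bias.

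A reader might infer that patency will certainly be understated. The documents do not support that. The downward direction needs scans missed at random and unscanned CD-TLR lesions counted as failures; section 5.2 implies the latter above the knee, but no evaluability rule states it. Below the knee, the phrasing in 5.2 leaves some doubt whether CD-TLR alone is failure.

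A reader might also infer that every CD-TLR is known. Section 7.9.1 lets subjects withdraw or be exited as lost to follow-up, and later CD-TLRs are then unseen. The asymmetry remains among those still followed.

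On materiality, the endpoint is secondary and descriptive, section 9.3 states that there are no primary hypotheses, the 12-month duplex is required, and the likely shift is small beside the sampling error. That is fair and keeps the severity low to moderate. The 9.5 bar on adjustment covers the primary analyses, so it does not block a different estimate for this secondary endpoint.

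**Conclusion.** The point holds in limited form. As written, 9.1 suits the two-part patency endpoint poorly when patency is a proportion: among followed subjects it removes only CD-TLR-free lesions, so it understates patency even when scans are missed purely at random. Over the assumed ranges the shift is about -0.7 to -7.3 points, for example 70% becoming 67.5% with t = 15% and m = 20%. Both size and direction rest on assumed rates, random missingness, and counting unscanned CD-TLR lesions as failures. Because other readings of the same text push the figure upward, the protocol needs an explicit rule. This is a low-to-moderate, inexpensive improvement and does not touch the primary endpoints.

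**What to change.** In section 9.1, exempt 12-month primary patency from the default and add the following:

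1. A CD-TLR through 12 months counts as failure whether or not a duplex was obtained.
2. Report the Kaplan-Meier freedom from CD-TLR at 12 months multiplied by the proportion duplex-patent among scanned CD-TLR-free units. The unit is the lesion above the knee and the flow pathway below the knee, as in 5.2.
3. Show the simple proportion with its exact interval alongside.
4. Report how many CD-TLR-free units were not scanned, and the bounds with all of them counted as patent and all as failed.
5. Use a subject-level bootstrap interval for the product only where both components have failures. Otherwise give an interval for each component, exact for the duplex proportion. With 10 of 10 below-the-knee units patent, a bootstrap would return 100-100%, whereas the exact lower limit is about 69%.

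The cost is a short paragraph of analysis text, a little more programming and a less simple interval for one secondary endpoint. The product still relies on scans being missing at random, which is why the bounds belong beside it. No visit, scan or treatment changes.
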